10.4. Reporting timelines

The sponsor-investigator will report to the National Competent Authority where the clinical investigation has commenced:

- all reportable events as described above which indicate an imminent risk of death, serious injury, or serious illness and that requires prompt remedial action for other patients/subjects, users or other persons or a new finding to it: immediately, but not later than 2 calendar days after awareness by sponsor of a new reportable event or of new information in relation with an already reported event.

EndoscoPic Submucosal Dissection using gel versus glycerol for submucosal injection: a randomized controlled multicentric trial (EPSILON)

Version 1 – dated 21/07/2021

- any other reportable events as described above or a new finding/update to it: immediately, but not later than 7 calendar days following the date of awareness by the sponsor of the new reportable event or of new information in relation with an already reported event.

1 PROTOCOL SUMMARY

Name of Finished Product/device: ORISE™ Gel	
Title of Study: EndoscoPic Submucosal dIssection using geL versus glycerOl for submucosal iNjection: a randomized controlled multicentric trial (EPSILON)	
Indication: Endoscopic resection by ESD of gastric and rectal superficial lesions	
Study centers: Erasme University Hospital Department of Gastroenterology, Hepatopancreatology and Digestive Oncology [name] Eveangelisches Krankenhaus, Teaching Hospital of Dusseldorf, Department of Internal Medicine [name] Cancer Center, Keio University School of Medicine Division of Research and Development for Minimally Invasive Treatment [name] Memorial Sloan Kettering Cancer Center [name]	
Number on participating Belgian Centers	1
Number of participating international centers	3
Studied period (years): Q4 2020-Q4 2023	Clinical Phase: Prospective, open-label, randomized (1:1), multicentric academic study
Hypotheses: Submucosal injection of ORISE™ Gel will shorten ESD procedure duration by improving lesion lifting and reducing the number of per-procedural bleedings.	
Study Design: A multicentric, randomized, open label prospective study: 
 • All subjects with indications of gastric and rectal ESD undergo screening and baseline visit • Informed consent is obtained when scheduling the ESD procedure • Randomization is made at the time of the ESD procedure after confirmation of the indication • ESD is performed using a 25 G needle, a dual-knife-J with glycerol (standard solution) or ORISE™ Gel in order to remove the lesion en-bloc. Additional saline injection through the electrosurgical knife will be left at the discretion of the endoscopist • A follow-up visit is scheduled at 2-4 weeks 	
Study visits:	

- Screening and baseline
- ESD procedure
- Post-treatment follow-up at 2 4 weeks

Number of patients (planned and analyzed): 133 patients by arm with a total of 266

Endpoints :

- Primary:

- Increase the dissection speed of the ESD procedure (defined as the dissected surface (mm²)/ESD duration (min). The dissected surface is defined as maximal diameter of specimen (mm) x perpendicular minimal diameter of specimen (mm) measured on ex-vivo pinned stretched specimen onto a cork. ESD duration is defined as the time from first submucosal injection to final cut time.

- Secondary:

- Total procedure duration (from scope insertion to scope retrieval) (min)
- Number of per-procedural bleeding (+ severity scale: oozing / severe non pulsating/ severe pulsating)
- total hemostatic time (addition of each hemostasis time for each per-procedural bleeding)
- Need for haemostatic forceps during ESD
- Difficulty of the dissection (scale)
- Amount of submucosal solution (glycerol or gel) used for ESD in ml
- Combined use of saline through the knife during ESD (number and ml)
- Number of needle injection dots during ESD (initially / during ESD)
- Need to adjust electrosurgical settings during ESD
- Clear visualisation of the plane of dissection during ESD (scale) (defined in the protocole)
- Rate of en-bloc dissection (defined as endoscopic resection of the targeted area in one bloc)
- Rate of complete endoscopic resection (defined as endoscopic evaluation of complete removal of the targeted area in the treated organ)
- Quality assessment of the pathological specimen (absolute measure of the depth of resected submucosa on the specimen, rate of clear (horizontal and vertical) margins)
- Adverse events:
 - Per-procedural (incidence of all adverse technical events during the procedure)
 - Early (clinical and laboratory at 24 h post procedure according to CTCAE v 5.0)
 - Late (clinical at 3 weeks follow-up)

Main criteria for inclusion and exclusion:

- Inclusion:

- Subject ≥18 years of age at the time of informed consent
- Patients must have given written informed consent
- Subjects with documented gastric or rectal lesions with indication of endoscopic removal by ESD, namely:
 - Gastric focal lesion with suspicion of early gastric cancer (low or high grade dysplasia with features of early gastric cancer; adenocarcinoma with

morphology of superficial lesion and work-up of superficial lesion)

- Rectal polyps (adenoma or superficial carcinoma) from 0 to 15 cm from the anal margin; with features being recognized indications of ESD: more than 20mm granular LST, more than 20mm non granular LST, more than 20mm villous or bulging polyps, Paris 0-IIa+IIc lesions, lesions with suspicious pattern (Kudo Vi / JNET 2B), lesions with anal canal involvement.

- Exclusion:

- Subjects who meet any of the following exclusion criteria cannot be enrolled in the study:
 - Gastric and rectal neuroendocrine tumour (NET) with indication of ESD will be excluded
 - Gastric and rectal lesions with indication of ESD but strong fibrosis due to previous partial resection will be excluded
 - Subject is currently enrolled in another confounding research
 - Subjects with any other location of ESD (esophagus, duodenum and colon) will not be included.

Support request: Glycerol or ORISE™ Gel will be ordered as other pharmaceuticals by the hospital and billed as locally done in routine practice. A collaborative research agreement between Boston Scientific and Erasme Hospital will be signed.

Procedures: Schedule of assessments in Table 1

Statistical Considerations: Sample size was computed using a two-sided Welch T-Test (groups with unequal variances) using an $\alpha = 0.05$ and a power of 80%.

2 INTRODUCTION

This statistical plan addresses the planned analyses for the study on the EPSILON on the protocol dated November 9, 2020. Specified analyses may be used for scientific presentation and/or manuscripts and may not all be provided to Competent Authorities.

3 ENDPOINT ANALYSIS

3.1 Primary Endpoint

Increase the dissection speed of the ESD procedure (defined as the dissected surface (mm²)/ESD duration (min)). The dissected surface is defined as maximal diameter of specimen (mm) x perpendicular minimal diameter of specimen (mm) measured on ex-vivo pinned stretched specimen onto a cork. ESD duration is defined as the time from first submucosal injection to final cut time.

3.1.1 Hypotheses

Based on available data of the dissection speed from Erasme, we calculated the dissection speed using the ORISE Gel and glycerol. These means and standard deviations are shown in the table below.

	Group Glyceol		Group Gel ORISE		Delta Speed (Gel - Glyceol)	
center	n	Speed (mm ² /min)	n	Speed (mm ² /min)	Speed (mm ² /min)	% of increase
Erasme	31	17.11 ± 18.27	10	22.24 ± 10.26	5.13 ± 4.61	23.06 %

A power analysis was performed using the results above to calculate the sample size. Using a two-sided Welch T-Test (groups with unequal variances) with an $\alpha = 0.05$ and power of 80%, with 1:1 randomization, 133 patients would be required to show a statistically significant difference between the groups. If this hypothesized difference is proven this would be a 23% increase in the speed of dissection. The results will also be stratified by site to see if any differences are observed, this will be performed using a generalized linear model.

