6.2. Sample size and randomization

Based on available data of the dissection speed from Erasme, we calculated the dissection speed using the Orise gel and glycerol. These means and standard deviations are shown in the table below.

EndoscoPic Submucosal Dissection using gel versus glycerol for submucosal injection: a randomized controlled multicentric trial (EPSILON)

Version 1 – dated 21/07/2021

	Group Glyceol		Group Gel ORISE		Delta Speed (Gel - Glyceol)	
center	n	Speed (mm ² /min)	n	Speed (mm ² /min)	Speed (mm ² /min)	% of increase
Erasme	31	17.11 ± 18.27	10	22.24 ± 10.26	5.13 ± 4.61	23.06 %

A power analysis was performed using the results above to calculate the sample size. Using a two-sided Welch T-Test (groups with unequal variances) with an $\alpha = 0.05$ and power of 80%, with 1:1 randomization, 133 patients would be required to show a statistically significant difference between the groups. If this hypothesized difference is proven this would be a 23% increase in the speed of dissection. The results will also be stratified by site to see if any differences are observed, this will be performed using a generalized linear model.

A computer-based block randomization scheme will be created using block randomization and stratifying by center and by organ type (stomach/rectum). Data will be collected through a printed CRFs and then anonymized and entered into a central web based secured platform.

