4.6 Subgroup Analyses

Stratified analyses will include tabulating the primary and select secondary endpoints by gender.

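### Randomisation is stratified by center and organ, but no planned analysis of dissection speed adjusts for both, and organ appears in none

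*SAP*

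**What the plan says.** Protocol 6.2 sets the allocation: "A computer-based block randomization scheme will be created using block randomization and stratifying by center and by organ type (stomach/rectum"). With one Belgian and three international centers, that makes 4 × 2 = 8 strata.

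For dissection speed, the analyses that can be found are these:

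- **Sample size (SAP section 1 and 3.1.1).** "Sample size was computed using a two-sided Welch T-Test (groups with unequal variances"). The Welch test has no covariates. It is named for sizing and is not declared the primary analysis.
- **Site (SAP 3.1.1 and Protocol 6.2).** "The results will also be stratified by site to see if any differences are observed, this will be performed using a generalized linear model". The word for addition makes this a supplement. Whether the model contains arm, or an arm-by-site term, is not said.
- **Subgroups (SAP 4.6).** "Stratified analyses will include tabulating the primary and select secondary endpoints by gender". Organ is not mentioned.

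The planning values come from one center: "Based on available data of the dissection speed from Erasme, we calculated the dissection speed using the ORISE Gel and glycerol". The organ mix of that pilot is not reported.

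SAP section 2 also ties the plan to another protocol date than the current one: "This statistical plan addresses the planned analyses for the study on the EPSILON on the protocol dated November 9, 2020". The protocol supplied is Version 1 of 21/07/2021.

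**The concern.** Stratified blocks keep center and organ almost balanced between the arms, so differences between strata drop out of the arm contrast. The Welch standard error does not know this. It is built from the total within-arm variance, which still includes the stratum differences. If those differences are real, the reported standard error overstates the true one, the confidence interval is too wide and the test rejects too rarely under the null. The estimate itself is unbiased.

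There are reasons to expect the strata to matter. The sponsor chose to balance on them. Protocol 8.2 lets sedation follow center experience, allows a different endoscope series in Japan, and uses different forceps sizes and coagulation power in stomach and rectum. None of this gives a value for the variance share.

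There is a second cost. In an open-label trial with no stated primary model, an unadjusted, a site-adjusted or a fully adjusted analysis could each be chosen after the data are seen.

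**Working it through.** **Inputs from SAP 3.1.1 and section 1.** Difference d = 22.24 − 17.11 = 5.13 mm²/min; SDs 18.27 (glycerol) and 10.26 (gel); two-sided α = 0.05; power 80%; n = 133 per arm, 266 in total.

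**Assumed, because the documents do not give it.** R² = share of the variance of speed explained by center and organ: 0.1, 0.2 and 0.3.

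**1. The plan's own figures.** Welch power from the noncentral t distribution is 79.9% at 132 per arm and 80.2% at 133, so 133 per arm reproduces. The pilot standard error also reproduces: √(18.27²/31 + 10.26²/10) = 4.61.

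The steps below use the normal approximation. S = 18.27² + 10.26² = 439.06; SE = √(439.06/133) = 1.817; d/SE = 2.82; power = 80.6% with no stratum effect.

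**2. Size of the conservatism.** With balanced strata, true variance / estimated variance = 1 − R².

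- SE inflation = 1/√(1 − R²)
- Type I error = 2·P(Z > 1.96/√(1 − R²))

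| R² | SE too large by | True type I error |
|---|---|---|
| 0.1 | 1.05 | 3.9% |
| 0.2 | 1.12 | 2.8% |
| 0.3 | 1.20 | 1.9% |

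**3. Power at 133 per arm.** Power = P(Z > 1.96·√(Vest/Vtrue) − d/√Vtrue). The answer depends on whether the pilot SDs already contain the stratum variance.

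- *Case A, all of it is in the pilot SDs.* Unadjusted: Vest = S/n, Vtrue = S(1 − R²)/n. Adjusted: both equal S(1 − R²)/n.
- *Case B, all of it comes on top.* Unadjusted: Vest = S/((1 − R²)n), Vtrue = S/n. Adjusted: both equal S/n.

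| R² | A unadjusted | A adjusted | B unadjusted | B adjusted |
|---|---|---|---|---|
| 0.1 | 82% | 85% | 78% | 81% |
| 0.2 | 83% | 88% | 74% | 81% |
| 0.3 | 85% | 92% | 68% | 81% |

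The gain is 2.7, 5.1 and 7.2 points in case A, and 3.0, 7.0 and 12.1 in case B.

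**4. Between the two cases.** Let a fraction f of the stratum variance T lie inside S. The residual variance is S − fT and the total is S + (1 − f)T. Setting unadjusted power to 80% gives f = 0.54, 0.62 and 0.63 for R² = 0.1, 0.2 and 0.3. Above these fractions the unadjusted test still has at least 80% power. A single-center pilot cannot contain between-center variance, so that part can only come on top. How much organ variance it contains is unknown.

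**5. Simulation check.** Setting: 4 centers × 2 organs, 133 per arm, additive stratum effects, HC3 standard errors, 6000 replicates per setting. Results for R² = 0.1 / 0.2 / 0.3:

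- Case A: unadjusted 82.6 / 83.3 / 85.0%, adjusted 84.6 / 88.1 / 91.6%.
- Case B: unadjusted 77.6 / 72.9 / 68.6%, adjusted 80.0 / 79.3 / 79.7%.
- Null rejection: unadjusted 3.7–3.8 / 2.5–3.2 / 1.8–1.9%; adjusted 4.4–5.4% throughout.

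**6. What an analysis by organ could show.** Assume a 50:50 split, so 66.5 per arm in each organ. The half-width of each organ-specific 95% CI is 1.96·√(439.06/66.5) = 5.04 mm²/min. The SE of the between-organ difference in effect is √(2 × 439.06/66.5) = 3.63. A between-organ difference of 5.13 would be detected with 29% power (25% at a 30:70 split).

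**The case against.** The error is on the safe side and rests on an R² that nobody has reported. If R² is near zero, nothing is lost. In case A the unadjusted test keeps more than the planned 80% power. The shortfall in case B comes mainly from sizing a four-center trial on single-center SDs; adjustment would offset it but did not cause it. Case B is also an extreme, since it puts the organ variance wholly outside the pilot. All of this is fair, and the top of the gain range should be read accordingly. The simulated gains are slightly lower than the formula gives: 2.0 to 6.6 points in case A and 2.4 to 11.1 in case B.

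The data shape matters too. Speed cannot be negative, yet the glycerol SD (18.27) exceeds its mean (17.11), so the distribution must be right-skewed. With log-normal speeds matching the pilot means and SDs, and multiplicative stratum effects explaining 10%, 20% and 30% of the log-scale variance, the raw-scale robust model gained only about 1, 2 and 4 points (79.5 to 80.7%, 80.3 to 82.2%, 83.1 to 86.9%). Those shares are on the log scale, so they are not comparable one for one with the tables above. The direction is unchanged: unadjusted Welch stays conservative and the adjusted test stays near 5%. The gain may simply be smaller.

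Finally, the site model may already contain arm, in which case center is adjusted for, and the SAP never calls Welch the primary test. Both points are right. They leave organ unaddressed in every analysis and the primary model unstated.

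**Conclusion.** The concern holds. The randomisation uses two stratification factors; the planned analyses of dissection speed use at most one of them, in a supplementary model with unstated terms, and organ in none. An unadjusted Welch analysis would be valid but conservative, with no bias and no inflation of false positives.

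What is lost is precision. For an assumed R² of 0.1 to 0.3, the confidence interval is 1.05 to 1.20 times as wide as it need be. The power given up is about 3 to 7 points if the pilot SDs include the stratum variance, up to 12 if they include none, and perhaps only 1 to 4 with strongly skewed data. Whether unadjusted power falls below 80% cannot be settled from the documents. Because the loss is conditional and conservative, this should be fixed but does not undermine the trial.

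The outdated protocol date in SAP section 2 is a minor document-control point. Nothing visible shows that the randomisation scheme differed in the November 2020 protocol.

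**What to change.** - **SAP 3.1.1:** state the primary analysis as a linear model of dissection speed on arm, center and organ, with heteroscedasticity-robust standard errors (for example HC3), reporting the arm difference with its 95% CI. The robust errors keep the protection against unequal variances for which Welch was chosen. Keep the unadjusted Welch test as a sensitivity analysis.
- **SAP 4.6:** add the treatment effect by organ with a CI, next to gender and labelled exploratory, given the low power for a between-organ difference.
- **SAP section 2:** cite the current protocol version and confirm that the plan matches its randomisation scheme.

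The cost is SAP wording only. Center and organ are known for every patient at randomisation, so no patients, visits or data are added. SAP 4.7 already provides for an amended plan approved before the analyses are run.

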4 ADDITIONAL DATA ANALYSES

4.1 Secondary Endpoints

- Total procedure duration (from scope insertion to scope retrieval) (min)
- Number of per-procedural bleeding (+ severity scale: oozing / severe non pulsating/ severe pulsating)
- Total hemostatic time (addition of each hemostasis time for each per-procedural bleeding)
- Need for haemostatic forceps during ESD
- Difficulty of the dissection (scale)
- Amount of submucosal solution (glycerol or gel) used for ESD in ml

- Combined use of saline through the knife during ESD (number and ml)
 - Number of needle injection dots during ESD (initially / during ESD)
 - Need to adjust electrosurgical settings during ESD
 - Clear visualisation of the plane of dissection during ESD (scale). The scale will be defined according the endoscopists evaluation of the delineation between the submucosa ad the underlying muscular layer:
 - Very-good visualization: clear delineation between the two layers with clear visualization of the blood vessels.
 - Good visualization: mostly clear delineation between the two layers, but with blurred regions
 - Bad visualization: delineation between the two layers is unclear (i.e.: fibrosis)
 - Rate of en-bloc dissection (defined as endoscopic resection of the targeted area in one bloc)
 - Rate of complete endoscopic resection (defined as endoscopic evaluation of complete removal of the targeted area in the treated organ)
 - Quality assessment of the pathological specimen (absolute measure of the depth of resected submucosa on the specimen, rate of clear (horizontal and vertical) margins)
 - Adverse events:
 - Per-procedural (incidence of all adverse technical events during the procedure)
 - Early (clinical and laboratory at 24 h post procedure according to CTCAE v 5.0)
 - Late (clinical at 2-3 weeks follow-up)
- 1) Evaluation of serious adverse events (SAEs) related to the device and/or the procedure through 30 days after the ERCP.

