10.3. Causality assessment

The relationship between the use of the medical device 13 (including the medical - surgical procedure) and the occurrence of each adverse event shall be assessed and categorized. During causality assessment activity, clinical judgement shall be used and the relevant

EndoscoPic Submucosal Dissection using gel versus glycerol for submucosal injection: a randomized controlled multicentric trial (EPSILON)

Version 1 – dated 21/07/2021

documents, such as the Investigator's Brochure, the Clinical Protocol or the risk Analysis Report shall be consulted, as all the foreseeable serious adverse events and the potential risks are listed and assessed there. The presence of confounding factors, such as concomitant medication/treatment, the natural history of the underlying disease, other concurrent illness or risk factors shall also be considered. The above considerations apply also to the serious adverse events occurring in the comparison group. For the purpose of harmonising reports, each SAE will be classified according to five different levels of causality. The sponsor and the investigators will use the following definitions to assess the relationship of the serious adverse event to the investigational medical device or procedures.

1. Not related: relationship to the device or procedures can be excluded when:
 - ✓ the event is not a known side effect of the product category the device belongs to or of similar devices and procedures;
 - ✓ the event has no temporal relationship with the use of the investigational device or the procedures;
 - ✓ the serious event does not follow a known response pattern to the medical device (if the response pattern is previously known) and is biologically implausible;
 - ✓ the discontinuation of medical device application or the reduction of the level of activation/exposure - when clinically feasible - and reintroduction of its use (or increase of the level of activation/exposure), do not impact on the serious event;
 - ✓ the event involves a body-site or an organ not expected to be affected by the device or procedure;
 - ✓ the serious event can be attributed to another cause (e.g. an underlying or concurrent illness/ clinical condition, an effect of another device, drug, treatment or other risk factors);
 - ✓ the event does not depend on a false result given by the investigational device used for diagnosis, when applicable;
 - ✓ harms to the subject are not clearly due to use error;

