 - ✓ In order to establish the non-relatedness, not all the criteria listed above might be met at the same time, depending on the type of device/procedures and the serious event.
2. Unlikely: the relationship with the use of the device seems not relevant and/or the event can be reasonably explained by another cause, but additional information may be obtained.
3. Possible: the relationship with the use of the investigational device is weak but cannot be ruled out completely. Alternative causes are also possible (e.g. an underlying or concurrent illness/ clinical condition or/and an effect of another device, drug or treatment). Cases where relatedness cannot be assessed or no information has been obtained should also be classified as possible.
4. Probable: the relationship with the use of the investigational device seems relevant and/or the event cannot reasonably explained by another cause, but additional information may be obtained.
5. Causal relationship: the serious event is associated with the investigational device or

EndoscoPic Submucosal Dissection using gel versus glycerol for submucosal injection: a randomized controlled multicentric trial (EPSILON)

Version 1 – dated 21/07/2021

with procedures beyond reasonable doubt when:

- ✓ the event is a known side effect of the product category the device belongs to or of similar
- ✓ devices and procedures;
- ✓ the event has a temporal relationship with investigational device use/application or procedures;
- ✓ the event involves a body-site or organ that
 - o the investigational device or procedures are applied to;
 - o the investigational device or procedures have an effect on;
- ✓ the serious event follows a known response pattern to the medical device (if the response pattern is previously known);
- ✓ the discontinuation of medical device application (or reduction of the level of activation/exposure) and reintroduction of its use (or increase of the level of activation/exposure), impact on the serious event (when clinically feasible);
- ✓ other possible causes (e.g. an underlying or concurrent illness/ clinical condition or/and an effect of another device, drug or treatment) have been adequately ruled out;
- ✓ harm to the subject is due to error in use;
- ✓ the event depends on a false result given by the investigational device used for diagnosis when applicable;

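### SAP 4.1's only SAE-specific item is limited to SAEs judged related by raters who know the arm; tabulate all SAEs by arm and correct the item's procedure and time window

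*SAP*

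**What the plan says.** SAP 4.1 lists the secondary endpoints as bullets and then adds one numbered item: "Evaluation of serious adverse events (SAEs) related to the device and/or the procedure", over a window of 30 days counted from an ERCP. No other part of the SAP plans an analysis of SAEs as such. Section 4.4 promises general descriptive summaries of post-procedure data. Section 5.1 defines an SAE by its seriousness, with no condition on relatedness, and gives rules for incomplete onset dates.

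The SAP summary describes the trial as "Prospective, open-label, randomized (1:1), multicentric academic study" and identifies the product under study as "Name of Finished Product/device: ORISE™ Gel". Protocol 10.3 says who judges causality: "The sponsor and the investigators will use the following definitions to assess the relationship of the serious adverse event". No masked or independent assessor is mentioned.

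Protocol 10.3 has five causality levels. The lowest (not related) and the highest (causal relationship) refer to the device or the procedures. The three between them (unlikely, possible, probable) refer only to the device; for example, "Possible: the relationship with the use of the investigational device is weak but cannot be ruled out completely". The same level takes the unclear cases: "Cases where relatedness cannot be assessed or no information has been obtained should also be classified as possible".

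Protocol 10.1 has all adverse events and SAEs collected from consent onward, whatever their cause.

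**The concern.** In a randomised trial, a count of all SAEs by arm is protected by the randomisation. A count of SAEs judged related is not, because a judgement made after randomisation, by people who know the treatment, decides which events enter it. If that judgement is stricter in one arm, the count can show a difference that does not exist or hide one that does.

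The plan leaves room for this in three ways. The raters know the arm. The middle causality levels are worded around a device that only one arm receives. And the SAP does not say which of the five levels count as related, so the count depends on an unstated cut-off that decides, among other things, whether unassessable cases placed in *possible* are included.

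The direction cannot be predicted. Device-centred wording could raise the count in the gel arm. The favourable early experience with the gel reported in the Protocol background (section 4) could lower it.

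**Working it through.** **1. The texts side by side**

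| Element | Text | Same for both arms? |
|---|---|---|
| SAP 4.1 filter | device or procedure | procedure limb yes; device limb gel only |
| Protocol 10.3, opening | device, with the procedure included | yes, through the procedure |
| Protocol 10.3, not related and causal | device or procedures | yes, through the procedure |
| Protocol 10.3, unlikely, possible, probable | device only | not as worded |
| Protocol 10.3, default to possible | no arm restriction | yes, but within a level worded for the device |
| Who judges | sponsor and investigators, open label | unmasked in both arms |

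The stated task is to judge the "relationship of the serious adverse event to the investigational medical device or procedures", but three of the five levels then drop the procedures. An SAE after glycerol can enter the count through the procedure. Whether a rater would grade it *possible* or *probable* on that basis is left to interpretation.

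**2. The plan's own figure**

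The documents attach no number to the SAE item. The only figure used below is 133 patients per arm (SAP 3.1.1), and it reproduces. With a difference of 22.24 − 17.11 = 5.13 and SDs of 18.27 and 10.26, the standard error at n = 133 is √((18.27² + 10.26²)/133) = √(439.06/133) = 1.817, so the noncentrality is 5.13/1.817 = 2.82. A two-sided Welch test at 0.05 then has 80.2% power, and 133 is the smallest n per arm that reaches 80%.

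**3. Effect of the filter**

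Let p be the true probability of an SAE and a the probability that an SAE is judged related, with at most one SAE per patient for simplicity. The expected number of patients counted per arm is 133 × p × a, and

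apparent risk ratio (gel/glycerol) = (p_gel × a_gel)/(p_gly × a_gly).

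If p is equal in both arms, it cancels and the ratio is a_gel/a_gly. With attribution **assumed** to lie between 50% and 90%:

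- 90% gel, 90% glycerol: 1.00
- 90% gel, 70% glycerol: 0.90/0.70 = 1.29
- 90% gel, 50% glycerol: 0.90/0.50 = 1.80
- 70% gel, 90% glycerol: 0.70/0.90 = 0.78
- 50% gel, 90% glycerol: 0.50/0.90 = 0.56

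In absolute terms, for the widest gap (90% in one arm, 50% in the other) and an **assumed** true SAE rate of 3% to 15% in both arms:

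| True rate | Patients with an SAE per arm | Counted at 90% | Counted at 50% | Apparent difference (percentage points) |
|---|---|---|---|---|
| 3% | 4.0 | 3.6 | 2.0 | 1.2 |
| 5% | 6.65 | 6.0 | 3.3 | 2.0 |
| 10% | 13.3 | 12.0 | 6.7 | 4.0 |
| 15% | 19.95 | 18.0 | 10.0 | 6.0 |

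The filter can also hide a true excess. With true rates of 10% (gel) and 5% (glycerol), and attribution of 50% and 90%, the counted rates are 5.0% and 4.5%. The apparent ratio is 0.050/0.045 = 1.11 against a true ratio of 2.0.

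An all-SAE count contains no a. With equal true rates its expected ratio is 1.00 whatever the raters believe.

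**4. The window in the same item**

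The item runs to 30 days after an ERCP. The trial's procedure is ESD, and Protocol 6.8 places the follow-up contact at weeks 2-4, that is, days 14 to 28. The last planned contact therefore falls 30 − 28 = 2 to 30 − 14 = 16 days before the stated window closes.

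**The case against.** The strongest case against runs as follows.

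- **The filter is not confined to the gel.** It includes the procedure, and every patient undergoes ESD. Protocol 10.3 opens by counting the procedure with the device and extends its considerations to SAEs in the comparison group. The notes in Protocol 10.2.1 cover events related to the comparator and to the procedures. On this view the device-only wording of the middle levels is loose drafting. This largely stands. A reader might infer that an unclear event defaults to related after gel and cannot be related after glycerol. The documents do not support that: the default to *possible* has no arm restriction, and a glycerol SAE can qualify through the procedure. What remains is that the judgement is unmasked and three levels are worded unevenly.

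- **Other safety endpoints are unfiltered.** The per-procedural, early and late adverse event endpoints carry no relatedness condition and will include many serious events. That stands, so it would be wrong to infer that the plan has no safety analysis free of attribution. But none of these endpoints separates events by seriousness, so they do not supply an SAE comparison.

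- **The item may be a leftover.** It is numbered after a bulleted list, names a procedure foreign to this trial, and is absent from Protocol 5.2.2, the Protocol synopsis and the SAP's own summary. It also mentions no comparison by arm. It may not be a deliberate choice. That is plausible, but it is the only SAE item in the SAP and would be followed as written.

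- **Nothing is lost.** All SAEs are collected (Protocol 10.1) and any SAE is reported to the authorities (Protocol 10.3). True, but collection and regulatory reporting are not a planned comparison. They show that the remedy is cheap.

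**Conclusion.** The concern holds in a limited form. The SAP's one SAE-specific item rests on an attribution made by raters who know the arm, against levels that are partly worded for one arm's product, with no stated cut-off. A related-only comparison could be distorted in either direction.

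The documents do not show that such bias exists, which way it would run, or how large it would be. The range of 0.56 to 1.80 for the apparent risk ratio under equal true rates follows from the assumed attribution limits of 50% and 90%. The counts rest in addition on assumed SAE rates of 3% to 15%. At those rates the widest attribution gap shifts the contrast by 1.2 to 6.0 percentage points, or about 2 to 8 patients (3.6 − 2.0 to 18.0 − 10.0). The procedure limb and the comparison-group sentence make a gap that wide less likely.

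The sample size and the primary analysis are unaffected. The mismatch of procedure and window in the same item needs no assumption, so the item has to be edited in any case.

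**What to change.** Replace the numbered item in SAP 4.1 with two lines.

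1. **Main SAE comparison.** All SAEs by randomised arm, regardless of attribution: number and percentage of patients with at least one SAE, and the risk difference with its 95% confidence interval. This fits the per-patient rule and the SAE definition already in SAP 5.1.
2. **Descriptive line.** SAEs judged related, with the five causality levels of Protocol 10.3 tabulated by arm. Showing every level removes the dependence on an unstated cut-off and makes any difference in attribution between arms visible.

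In the same edit, reconcile the reference to ERCP and the 30-day window with the ESD procedure and the 2-4 week follow-up in Protocol 6.8. The sponsor should settle which window is meant and state it the same way in both documents.

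The cost is an SAP amendment, which SAP 4.7 provides for if approved before the analyses are performed, and one extra table. All SAEs are already collected under Protocol 10.1, so no new data or patients are needed.
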